6.3. Adjustments for Covariates

The study is stratified by country, baseline HbA1c ($\leq 8.5\%$, $> 8.5\%$ [≤ 69 , > 69 mmol/mol]), and use of concomitant oral antidiabetic medications (metformin alone, metformin plus SU). For HbA1c related analyses, country and concomitant oral antidiabetic use will be used as stratification factors and baseline HbA1c as a covariate. For other efficacy analyses, country, baseline HbA1c ($\leq 8.5\%$, $> 8.5\%$ [≤ 69 , > 69 mmol/mol]), and use of concomitant oral antidiabetic medications (metformin alone, metformin plus SU) will be used as stratification factors and respective baseline value as a covariate.

6.4. Handling of Dropouts or Missing Data

For analyses using in EAS, missing data will be addressed by using a mixed-effect model repeated measures (MMRM) analysis for continuous longitudinal variables. The MMRM model provides consistent estimator when data is missing at random. The model implicitly adjusts for missing data through a variance-covariance structure. For health outcomes data, LOCF will be used for Analysis of Covariance (ANCOVA) analysis and item-level missingness is dealt with as per instrument developers' instruction.

For analyses using FAS, data for patients with missing values at the 40-week visit will be imputed based on the method described in Section [6.12.1.3](#). Unless specified otherwise, imputation of missing data will be limited to primary and key secondary efficacy endpoint analyses.

Missing other secondary or exploratory efficacy parameter values and missing safety laboratory values will not be explicitly imputed.

6.5. Multicenter Studies

GPHO is a multi-country, multi-site study. Site will not be analyzed as a fixed effect in any of the models so pooling strategies will not be required.

6.6. Multiple Comparisons/Multiplicity

Type 1 Error rate control strategy for primary and key secondary efficacy objectives is illustrated in Section [6.12.3](#). No multiplicity adjustments will be made for evaluating other secondary and exploratory efficacy objectives and safety assessments.

6.7. Patient Disposition

A listing of final study disposition and a listing of randomized treatment assignment (planned treatment) for all randomized patients will be provided. Final study disposition and study drug disposition for all randomized patients will be summarized by planned study treatment.

6.8. Patient Characteristics

A listing of patient demographics will be provided. All demographic and baseline clinical characteristics will be summarized by study treatment for the patients in all randomized population and mITT population. Baseline demographic and clinical characteristics of special

interest including but not limited to: age, gender, race, BMI, weight, country of enrollment, HbA1c, fasting serum glucose, duration of T2DM, baseline antihyperglycemic medication, renal function, history of retinopathy, results of the fundoscopic exam, and history of gallbladder disease.

6.9. Concomitant Therapy

Prespecified concomitant medications of interest will be summarized by treatment at randomization. Additionally, medications of interest initiated after randomization will be summarized. Concomitant therapies will be mapped using the World Health Organization (WHO) Drug Dictionary in the clinical trial database and will be further classified using Anatomic-Therapeutic-Chemical (ATC) codes for reporting purposes.

The concomitant medications of interest include the following groups of medication:

- baseline Antihyperglycemic therapy
 - Prior glucagon-like peptide-1 receptor agonist (GLP-1 RA) use by type
 - Metformin
 - Sulfonylureas, by type
- baseline antihypertensive therapy, by type
- baseline lipid lowering therapy, by type
- changes to baseline medication in Study Period II:
 - Antihypertensive therapy
 - Lipid lowering therapy
- changes to baseline medication in Study Periods II and III:
 - antihyperglycemic therapy
- rescue therapy due to severe persistent hyperglycemia
- utilization of:
 - antidiarrheal medication
 - antiemetic medication

6.10. Treatment Exposure and Compliance

A listing of patients randomized but not receiving study treatment will be provided, if applicable. The listing will include patient identification, randomized treatment arm, and the reason for not receiving study treatment.

A listing of randomized patients who had inadvertently received incorrect study treatment anytime during the study will be provided, if applicable. The listing will include patient identification, randomized treatment arm, and information related to the treatment incorrectly

received: incorrectly received study treatment, start and stop dates during which the incorrect treatment was received.

Summary of duration of follow-up (defined as time in days from date of randomization to date of safety follow-up visit) and duration on study treatment (defined as time in days from date of first dose of study treatment to date of last dose of study treatment plus 7 days) will be provided by therapy.

6.10.1. Exposure and Compliance to Tirzepatide

The number of patients prematurely discontinuing study treatment prior to the 40-week visit will be provided by study treatment. Reasons for prematurely discontinuing study treatment prior to the 40-week visit will also be provided by study treatment. A time-to-event analysis of premature study treatment discontinuation will be conducted.

The proportion of patients with missing dosing information, receiving no LY dose, receiving 2.5 mg, 5 mg, 7.5 mg, 10 mg, 12.5 mg or 15 mg will be presented by randomized treatment and week from first dose.

A listing and summary of patients continuing on a reduced maintenance dose of tirzepatide compared to the randomized dose will be provided.

Compliance will be defined as taking at least 75% of the scheduled tirzepatide doses. Compliance will be calculated by taking the number of doses administered (regardless of the actual dose administered) divided by the total number of doses expected to be administered $\times 100$. Treatment compliance will be summarized descriptively over the entire study period by treatment using the mITT population.

6.10.2. Exposure and Compliance to Insulin Glargine Treat-to-Target Algorithm

Summary information on total daily dose of insulin glargine will be reported by visit. Information related to compliance to treat-to-target therapy including reasons for non-compliance will be summarized.

Compliance will be defined as taking at least 75% of the scheduled insulin doses. The number of insulin doses administered was calculated by subtracting the number of doses missed as entered in the compliance CRF from the number of doses expected to be administered. Compliance will be calculated by taking the number of doses administered (regardless of the actual dose administered) divided by the total number of doses expected to be administered $\times 100$. Treatment compliance will be summarized descriptively over the entire study period by treatment using the mITT population

Additionally, summaries will be produced for the percent of patients to reach fasting serum glucose goals of <100 mg/dL (5.6 mmol/L) and <126 mg/dL (7 mmol/L) over time at weeks 16, 24, and 40.

6.11. Important Protocol Deviations

Important protocol deviations are identified in the Trial Issues Management Plan (TIMP). A listing and a summary of important protocol deviations by treatment will be provided.

6.12. Efficacy Analyses

6.12.1. Primary Efficacy Analysis

The primary efficacy measure will be change in HbA1c from baseline (postbaseline – baseline). Both HbA1c values as well as change from baseline in HbA1c will be summarized by treatment and nominal visit (week). If scheduled HbA1c data at the primary endpoint visit are not available, unscheduled HbA1c data collected for the primary endpoint visit will be included in the analysis.

6.12.1.1. Primary Analysis Model

The analysis will be conducted utilizing HbA1c data in EAS from baseline through the 40-week visit with the aid of a mixed model for repeated measures (MMRM). Restricted maximum likelihood (REML) will be used to obtain model parameter estimates and Kenward-Roger option will be used to estimate denominator degrees of freedom. The response variable of the MMRM model will be the primary measure and model terms will include treatment, visit, treatment by visit interaction, country, and baseline concomitant oral antihyperglycemic medication use (metformin alone versus metformin plus SU) as fixed effects, and baseline HbA1c as a covariate. An unstructured covariance structure will be used to model the within-patient errors. If this model fails to converge, the following covariance structures will be tested in order:

- heterogeneous Toeplitz;
- heterogeneous First Order Autoregressive;
- heterogeneous Compound Symmetry;
- Toeplitz;
- first Order Autoregressive;
- compound Symmetry.

The first covariance structure that converges will be used. The resulting least squares mean (LSM) estimates of mean change from baseline in HbA1c will be plotted by visit and by study treatment.

With the aid of the MMRM analysis, 2-sided 97.5% confidence interval (CI) for mean change in HbA1c from baseline to 40-week visit for (10 mg tirzepatide - insulin glargine) as well as for (15 mg tirzepatide - insulin glargine) will be derived. If the upper limit of the CI is $\leq 0.4\%$, then the respective dose of tirzepatide (10 mg and/or 15 mg) will be declared noninferior to insulin glargine relative to change in HbA1c from baseline.

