7.7.2. Severe, Persistent Hyperglycemia

Add-on glycemc rescue therapy will be allowed for patients who meet prespecified criteria for severe, persistent hyperglycemia described below and no intercurrent cause of the hyperglycemia could be identified (investigators should first confirm that the patient is fully compliant with the assigned therapeutic regimen and that he or she does not have an acute condition causing severe hyperglycemia):

- (a) average daily BG from the once-weekly 4-point SMBG profile >270 mg/dL (>15.0 mmol/L) over at least a consecutive 2-week period any time during the first 8 weeks post randomization;
OR
- (b) average daily BG from the once-weekly 4-point SMBG profile >240 mg/dL (>13.3 mmol/L) over a consecutive 2-week period at any time 9 to 16 weeks post randomization;
OR
- (c) average daily BG from the once-weekly 4-point SMBG profile >200 mg/dL (>11.1 mmol/L) over a consecutive 2-week period at any time beyond the first 16 weeks post randomization;
OR

- (d) HbA1c \geq 8.5% at 24 weeks, with inadequate response to the existing regimen defined as improvement in HbA1c over the last 3 months (week 12 to week 24) that is $<$ 0.3%.

Rescue therapy option:

For the insulin glargine group, patients can further titrate the insulin glargine. The criteria described above for severe, persistent hyperglycemia will only be applicable after Week 16. The first choice before initiating any rescue therapy for those patients during the initial 16 weeks will be to follow the TTT algorithm to increase the dose of insulin glargine.

Rescue treatment with GLP-1 receptor agonists, DPP-4 inhibitors, fixed-dose combination with component of GLP-1 receptor agonists or DPP-4 inhibitors, or pramlintide will not be allowed. Additionally, use of other basal insulins will not be allowed in the insulin glargine group. Use of glargine will not be allowed in the tirzepatide groups.

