10.3.3. Efficacy Analyses

10.3.3.1. Primary Analyses

The primary objective of this study is to establish noninferiority of 10 mg tirzepatide and/or 15 mg tirzepatide to insulin glargine relative to mean change in HbA1c from baseline to the 40-week visit.

The primary efficacy analysis will be based on the contrast from the MMRM analysis using EAS. The response variable of MMRM will be change in HbA1c from baseline values obtained at each scheduled postbaseline visit. The independent variables of the MMRM model are treatment group (5 mg tirzepatide, 10 mg tirzepatide, 15 mg tirzepatide, and insulin glargine), visit, and treatment-by-visit interaction, country, sulfonylurea use (Yes or No), and baseline HbA1c as a covariate. An unstructured covariance structure will model relationship of within-patient errors. If the analysis fails to converge, the following variance-covariance matrices will be used (in order) until convergence is achieved: heterogeneous compound symmetry, compound symmetry, and first-order autoregressive. The Kenward-Roger approximation will be used to estimate denominator degrees of freedom. With the aid of the MMRM analysis, 2-sided 97.5% CIs for the difference in mean change in HbA1c from baseline to the 40-week visit between 10 mg tirzepatide and insulin glargine as well as between 15 mg tirzepatide and insulin glargine will be constructed. If the upper limit of the CI is below 0.4%, the tirzepatide dose will be declared noninferior to insulin glargine.

Additional details, including analysis methods for key secondary endpoints and a strategy for controlling the overall family-wise type 1 error rate at an alpha of 0.05 for primary and key secondary endpoint evaluation will be provided in the SAP.

Additional Analysis for the Primary Endpoint

The primary analysis model, MMRM, will be repeated using the PP populations to check the sensitivity of the analysis. If the conclusion differs from that of all randomized patients, the data and analyses will be further investigated. Details for the analysis conducted on PP population will be included in SAP.

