5.2. Determination of Sample Size

Although the primary objective of the trial is to demonstrate that once-weekly tirzepatide 10 mg and/or 15mg doses are non-inferior to titrated insulin glargine relative to mean change in HbA1c from baseline, the trial is powered to assess superiority of tirzepatide 10 mg and 15mg, each tested in parallel against titrated insulin glargine at two-sided significance level of 0.025, relative to the primary endpoint (mean change in HbA1c from baseline at 40 weeks), under the following assumptions: use of 2-sample t-test utilizing HbA1c data collected before initiation of any rescue medication or premature treatment discontinuation with no more than 25% subjects initiating any rescue medication or premature treatment discontinuation in each treatment group; 0.45% greater mean reduction in HbA1c from baseline for 10mg and 15mg tirzepatide compared to insulin glargine; 1:1:1:1 randomization; and a common standard deviation (SD) of 1.2%. On the basis of these assumptions, approximately 956 patients (80% from China, 20% from other countries/regions) with type 2 diabetes will be enrolled into this study to ensure at least 90% power to demonstrate that tirzepatide 10mg and/or 15mg are superior to insulin glargine relative to the primary endpoint. Using the same assumptions would provide >99% power for the non-inferiority comparison. China patients would provide 82% power to demonstrate the superiority.

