5.3. Method of Assignment to Treatment

Approximately 956 Patients who meet all criteria for enrollment will be randomized to one of the study treatment arms at Visit 3. Assignment to treatment arms will be determined by a computer-generated random sequence using an interactive web response system (IWRS). Patients will be randomized in a 1:1:1:1 ratio to receive 5 mg tirzepatide, 10 mg tirzepatide, 15 mg tirzepatide, or insulin glargine. The randomization will be stratified by country, baseline HbA1c concentration ($\leq 8.5\%$, $> 8.5\%$ [≤ 69 , > 69 mmol/mol]), and use of concomitant oral antidiabetic treatments (Metformin alone, metformin plus sulfonylurea).

6. A Priori Statistical Methods

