6.2. General Considerations

Statistical analysis of this study will be the responsibility of Eli Lilly and Company (Lilly) or its designee. All statistical analyses will be conducted with SAS Version 9.4 or higher unless otherwise stated. Any change to the data analysis methods described in the protocol will require an amendment only if it changes a principal feature of the protocol. Any other changes to the data analysis methods described in the protocol, and the justification for making the change, will be described in the SAP or the clinical study report (CSR). Some analyses and summaries described in this analysis plan may not be conducted if not warranted by data (e.g., few events to justify conducting an analysis). Listings of events will be provided in such situations.

Additional analyses of the data may be conducted as deemed appropriate without further changes made to the protocol or SAP, even after the primary or final database locks (DBL).

Patients inadvertently receiving incorrect study treatment are expected to switch to their randomized treatment arm as soon as possible. Patients assigned to tirzepatide may not be able to tolerate the maximum dose of the randomized treatment arm and may continue study participation on a reduced maintenance dose. Continuing on a reduced maintenance dose will neither be considered as discontinuation of randomized treatment nor will be considered as non-

compliant to randomized treatment. Additionally, to avoid potential selection biases, unless stated otherwise, statistical summaries and analyses will be conducted based on randomized maintenance dose regardless of the actual treatment received by the patient.

Last available measurement during Visit 1 to Visit 3 (including unscheduled visits) prior to or on the first dose day will serve as baseline. Immunogenicity, urinary albumin to creatinine ratio, lipid values, and health outcome measures obtained at Visit 3, regardless of the timing relative to first dose, will be used as baseline.

Efficacy and safety will be assessed using the modified intent-to-treat (mITT) population, which consists of all randomly assigned participants who are exposed to at least one dose of study drug. The primary and multiplicity adjusted objectives, will be performed on EAS and FAS. When change from baseline is included as a response variable of analysis models, the patient will be included in the analysis only if he/she has a baseline and a postbaseline measurement.

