6.12.2.3. Proportion of Patients Achieving HbA1c $<7\%$ at the 40 week Visit

The analysis will be conducted utilizing data using the EAS with missing values imputed from an MMRM model and then dichotomized. The MMRM model includes treatment, country, baseline concomitant oral antihyperglycemic medication use, visit, and treatment-by-visit interaction as fixed effects, and baseline HbA1c as a covariate. After dichotomizing continuous HbA1c, the data are analyzed using a logistic regression model with treatment, country, and baseline concomitant oral antihyperglycemic medication use as fixed effects, and baseline HbA1c as a covariate. In addition, longitudinal logistic regression with repeated measurements with country, baseline concomitant oral antihyperglycemic medication use, treatment, visit, and treatment-by-visit interaction as fixed effects, and baseline HbA1c as a covariate will also be provided using data in EAS. If the longitudinal logistic model does not converge due to a small number of events, logistic regression will be utilized to analyze the proportion of patients achieving HbA1c $<7\%$ at nominal visits.

Analyses also will be conducted utilizing HbA1c data in the FAS at baseline and at the 40-week visit with the aid of a logistic regression with multiple imputation of missing HbA1c data at the 40-week visit (see Section 6.12.1.3 for details). Model terms will include treatment, country, and baseline concomitant oral antihyperglycemic medication use as fixed effects, and baseline HbA1c as a covariate. Statistical inference over multiple imputations will be guided by Rubin (1987).

6.12.3. Type 1 Error Rate Control Strategy for Primary and Key Secondary Efficacy Analysis.

Type 1 error rate control strategy for evaluation of primary and key secondary objectives is illustrated in

Figure GPHO.6.1.

1. $H_{15,1}$, $H_{15,2}$, and $H_{15,3}$ are evaluated hierarchically each at a 2-sided 0.025 significance level conditioned on successfully achieving the preceding objective. In parallel,
2. $H_{10,1}$, $H_{10,2}$, and $H_{10,3}$ are evaluated hierarchically each at two-sided 0.025 significance level conditioned on successfully achieving the preceding objective.
3.
 - a) If all objectives in #1 and #2 above are successfully established, $H_{5,1}$, $H_{5,2}$, and $H_{5,3}$ are evaluated hierarchically, each at a 2-sided 0.05 significance level.

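### The primary MMRM fits one baseline-HbA1c slope for all visits; if that slope steepens by Week 40 the Week 40 interval is wider than it need be, and a baseline-by-visit term avoids this at no measurable statistical cost.

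*SAP*

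**What the plan says.** SAP 6.12.1.1 gives the fixed effects of the primary model: "model terms will include treatment, visit, treatment by visit interaction, country, and baseline concomitant oral antihyperglycemic medication use". The list ends "as fixed effects, and baseline HbA1c as a covariate". The covariance is unstructured, estimated by REML with Kenward-Roger degrees of freedom.

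Protocol 10.3.3.1 has the same structure: "visit, and treatment-by-visit interaction, country, sulfonylurea use (Yes or No), and baseline HbA1c as a covariate". The Protocol synopsis and 10.3.1 agree. No section adds a baseline-by-visit term or discusses whether the slope is constant.

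The model that fills in missing HbA1c for the <7% endpoint (SAP 6.12.2.3) has the same form: "The MMRM model includes treatment, country, baseline concomitant oral antihyperglycemic medication use, visit, and treatment-by-visit interaction as fixed effects", with baseline HbA1c again entered once. The body-weight model (SAP 6.12.2.2) is built on the primary model.

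The one HbA1c-change model with a slope specific to Week 40 is the ANCOVA in SAP 6.12.1.2. That is a sensitivity analysis on the full analysis set with multiple imputation.

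**The concern.** Treatment effects and the covariance vary freely by visit, but the covariate likely to predict most is held to one slope. The schedule makes a changing slope plausible. All tirzepatide patients are on 2.5 mg until Week 4, the 15 mg arm escalates until Week 20, and glargine titration takes place mainly in the first 16 weeks. If little has changed by Week 4, baseline has little change to predict; by Week 40 it may have much more. This is an inference, not a figure in the documents.

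Under an unstructured covariance the common slope is a precision-weighted average, and the early, less variable visits dominate it. The part of the Week 40 slope that it misses goes into the Week 40 residual variance. At stake are:

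- the width of the reported intervals for HbA1c non-inferiority and superiority;
- the accuracy of individual predictions in the <7% imputation, an endpoint within the Type 1 error strategy.

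**Working it through.** **1. The plan's own figures.** SAP 5.2 gives a difference of 0.45, "a common standard deviation (SD) of 1.2"%, two-sided alpha 0.025, 239 per arm and at most 25% lost to rescue or discontinuation.

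- Evaluable per arm: 239 × 0.75 = 179.25.
- SE = 1.2 × √(2/179.25) = 0.1268; half-width of the 97.5% interval = 2.2414 × 0.1268 = 0.284.
- Superiority power: Φ(0.45/0.1268 − 2.2414) = 90.5% (stated: at least 90%).
- China alone: 179.25 × 0.80 = 143.4 per arm, power 82.5% (stated 82%).
- Non-inferiority: the distance to the margin is 0.40 + 0.45 = 0.85, power above 99.99% (stated >99%).

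The design figures reproduce. They rest on an unadjusted t-test.

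**2. Formula for the loss.** Let s be the vector of true visit slopes, S the residual covariance and SDb the baseline SD.

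- Common slope: b = (1′S⁻¹s)/(1′S⁻¹1).
- Extra Week 40 variance: (s40 − b)² × SDb².
- Inflation: that amount divided by Var(Y40 | baseline) = 1.44 − s40² × SDb².

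**3. One case by hand.** Assume slopes from -0.2 to -0.6 and SDb 0.76. A simulated REML fit (956 patients, 7 visits, about 25% loss, stratified randomization, 115 runs) gave b = -0.19.

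- Extra variance: (0.60 − 0.19)² × 0.76² = 0.097.
- Var(Y40 | baseline): 1.44 − 0.36 × 0.5776 = 1.232.
- Inflation: 0.097/1.232 = 7.9%, so the SE ratio is √1.079 = 1.04. The simulation itself gave 1.036.
- Total common-slope variance: 1.232 + 0.097 = 1.329, below 1.44.

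Other simulated SE ratios (common slope over by-visit): 0.9996 for a constant -0.5; 1.009 for -0.3 to -0.5; 1.089 for -0.2 to -0.8; 1.070 for -0.2 to -0.6 with baseline SD 1.01.

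**4. Grid.** There are 81 settings per slope pair. The total Week 40 SD of 1.2 comes from the SAP. The following are assumed: baseline SD 0.80, 0.875 or 0.95; AR(1) correlation 0.70, 0.775 or 0.85; Week 4 residual SD 0.4, 0.5 or 0.6, rising log-linearly to Week 40; intermediate slopes linear, logarithmic or flat from Week 24.

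| Slope, Week 4 to Week 40 | Week 40 variance inflation, min / median / max |
|---|---|
| -0.5 to -0.5 | 0 / 0 / 0% |
| -0.4 to -0.6 | 1.1 / 2.1 / 3.9% |
| -0.3 to -0.6 | 2.6 / 4.7 / 8.7% |
| -0.2 to -0.7 | 7.3 / 13.7 / 26.3% |
| -0.15 to -0.7 | 8.9 / 16.6 / 31.8% |

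These are variances; the effect on interval width is about half as large. The common-slope variance is at most 1.36 anywhere in the grid, against 1.44 planned.

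**5. Stratification and missing data.** "The randomization will be stratified by country, baseline HbA1c concentration" (SAP 5.3), with a cut at 8.5%. This balances baseline between arms, so the common-slope estimate varies less than its reported SE implies. A second simulation used 600 replicates, two arms of 239, baseline truncated to 7.5-11.0 (SD 0.84), 20% random discontinuation, and censoring by the Week 24 rescue rule in Protocol 7.7.2 (HbA1c at least 8.5%, "with inadequate response to the existing regimen defined as improvement in HbA1c over the last 3 months" of less than 0.3%). Missingness was 27-29%.

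| Slopes | Reported SE ratio | True sampling SE ratio |
|---|---|---|
| equal | 1.00 | 1.00 |
| -0.3 to -0.6 | 1.03 | 1.02 |
| -0.2 to -0.7 | 1.08 | 1.05 |

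**6. Bias in the contrast.** The paired difference, common minus by-visit, is -0.007 (-0.3 to -0.6) and -0.010 (-0.2 to -0.7) when discontinuation is unrelated to baseline. It becomes material only if discontinuation depends on baseline in opposite directions by arm. With risk multiplied per SD by 0.61 on tirzepatide and 1.65 on glargine it is -0.049 and -0.080; reversed, +0.040 and +0.065.

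**7. The <7% imputation.** For a patient 1 SD (0.84) above mean baseline, imputed Week 40 HbA1c is too high by the amounts below. The error is zero at mean baseline or with equal slopes, and changes sign below the mean.

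| Last visit | -0.3 to -0.6 | -0.2 to -0.7 |
|---|---|---|
| Week 8 | 0.23 | 0.37 |
| Week 16 | 0.19 | 0.31 |
| Week 24 | 0.12 | 0.19 |

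In the 0.61/1.65 pattern of step 6, the imputed between-arm difference in the proportion below 7% is off by 1.1 to 1.6 percentage points.

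**The case against.** The strongest reply is that nothing here is an error. The protocol and SAP agree on the baseline term, the model is fully specified, and randomization protects the contrast. The loss depends on slopes, a baseline SD and correlations that the documents do not give. Milder steepening costs little: -0.3 to -0.5 adds about 1% to the SE. With baseline SD at 0.70-0.84, median variance inflation falls to about 3% for -0.3 to -0.6 and about 8% for -0.2 to -0.7. Part of the widening is conservatism rather than lost precision. The larger bias figures need a discontinuation pattern that nothing in the documents supports, and the simulated missingness slightly exceeds the planned maximum of 25%. The Week 40 ANCOVA already fits its own slope.

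Most of this stands, and it limits the point to efficiency. It does not remove the point. The ANCOVA uses different data and imputation, so it does not replace the primary estimate. The uncertainty about slopes also favours the added term: every steepening pattern examined showed a gain, and equal slopes showed no measurable loss.

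**Conclusion.** The point holds as a conditional matter of efficiency. If the slope on baseline HbA1c steepens between Week 4 and Week 40, the reported Week 40 interval is about 1% to 9% wider than with a baseline-by-visit term, depending on assumed slopes and baseline SD. If the slopes are equal, the two models give the same interval.

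The planned power is not harmed, because it is calculated without baseline adjustment and the common-slope variance stays below 1.44. Only if 1.2 were read as the residual SD after by-visit adjustment would power fall below 90% (87.9% at an SE ratio of 1.04), and SAP 5.2 does not describe it that way. Non-inferiority power stays above 99.9% throughout. Bias in the contrast is about 0.01 or less unless discontinuation depends on baseline differently by arm. In the <7% imputation the effect is a baseline-related shift in individual predictions. The change should be made because it is close to free, not because a planned conclusion is in danger.

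**What to change.** Add a baseline HbA1c-by-visit term to the primary MMRM in SAP 6.12.1.1 and to the imputation MMRM in SAP 6.12.2.3. Bring Protocol 10.3.3.1 into line, or record the reason for the departure as SAP 6.2 provides: a change of method "and the justification for making the change, will be described in the SAP" or the study report. An amendment is needed only if the sponsor regards the term as a principal feature of the protocol. A baseline weight-by-visit term could be added to the body-weight model (SAP 6.12.2.2) in the same way; the gain there has not been quantified.

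The cost is six parameters (seven slopes in place of one) and no new data. In the simulation with a constant slope the common-to-by-visit SE ratio was 0.9996, so the term widened the interval by about 0.04%.
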